#### 9.1.4 Classification

##### 9.1.4.1 Severity (based on Clavien classification)

Each adverse event should be assessed for its severity, or the intensity of an event experienced by the subject.

- **Mild:** Awareness of a sign or symptom that does not interfere with the subject's activity or is transient resolved without treatment and has no sequelae.
- **Moderate:** May interfere with the subject's usual activity and require additional intervention and/or treatment, and may have additional sequelae.
- **Severe:** Significant discomfort to the subject and/or interferes with the subject's activity. Additional intervention and or treatment are necessary. Additional sequelae occur. Severe is used to describe the intensity of an event experienced by the subject.

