#### 5.1.2 Safety:

##### 5.1.2.1 Intraoperative complications

- Complications according to Clavien scale
- Conversion to TURP to maintain hemostasis (procedure completed with laser)
- Conversion to TURP to complete procedure
- Capsule perforation
- Blood loss (blood transfusion, pre and post-operative hemoglobin and hematocrit)

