# **8 Study Analysis Plan**

## **8.1 Study Analysis**

The results of the study: subject demographics, baseline assessments, treatment parameters, treatment evaluations and follow-up assessments will be summarized and descriptive analysis will be performed. Adverse events reported will be listed, documenting course, outcome, severity, and possible relationship to the treatment. The modified Clavien classification will be used to evaluate severity of Adverse Events [2].

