#### **9.1.2 Adverse Device Effect**

Adverse event related to the use of an investigational medical device. Adverse Device Effect can be an anticipated serious adverse Device Effect which by its nature, incidence, severity or outcome has been identified in the risk analysis report or unanticipated if it has not been identified in the risk analysis report.

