#### **9.1.3 Serious Adverse Events**

NOTE: The term serious is not synonymous with severity, which may be used to describe the intensity of an event experienced by the subject. An AE that does not meet any of the below criteria will be classified as non-serious.

A serious adverse event is any event that:

4. led to death,
5. led to serious deterioration in the health of the subject, that either resulted in:
  - 5.1. a life-threatening illness or injury, or
  - 5.2. a permanent impairment of a body structure or a body function, or
  - 5.3. in-patient or prolonged hospitalization, or
  - 5.4. medical or surgical intervention to prevent life-threatening illness or injury or permanent impairment to a body structure or a body function,
6. led to foetal distress, foetal death or a congenital abnormality or birth defect

Any adverse events or complications reported by the patient or observed by the physician that occur during or after treatment with the device will be recorded in the medical record or source document and on the dedicated Case Report Form. The investigator will determine if the AEs are device related or procedure related. This assessment shall include the onset date, resolution date, severity, seriousness, frequency, additional treatment required and outcome.

Each adverse event should be assessed according to the following criteria:

**Description: Surgical. Protocol LUM-SBU-VP-15-02, Ablation efficacy of contact side firing fiber in predefined settings for treating BPH**

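### The adverse event criteria in section 9.1.4 give no Clavien grade or mapping, no category for a likely causal link, and no device-based definition of *Device* (minor)

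*Combined protocol and SAP*

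**What the plan says.** **Analysis and endpoint.** Section 8.1 states: "The modified Clavien classification will be used to evaluate severity of Adverse Events", citing reference 2. It also plans a listing of adverse events "documenting course, outcome, severity, and possible relationship to the treatment". Section 5.1.2.1 (and the synopsis) has "Complications according to Clavien scale" as one of the primary safety endpoints.

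**Severity at the site.** Section 9.1.3 instructs: "Each adverse event should be assessed according to the following criteria". The severity criteria that follow, in 9.1.4.1, are headed "Severity (based on Clavien classification". They are *Mild*, *Moderate* and *Severe*, described as the intensity of the event as the subject experiences it. Section 9.1.3 also requires seriousness, additional treatment and outcome to be recorded for each event.

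**Relatedness.** Section 9.1.3 says: "The investigator will determine if the AEs are device related or procedure related". Section 9.1.4.2 then offers two attributions (*Device*, *Procedure*) and four levels of certainty (*Definitely Related*, *Possibly Related*, *Not Related*, *Unknown*). Section 9.1.2 defines an adverse device effect as: "Adverse event related to the use of an investigational medical device".

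**The concern.** The scale named for the analysis and the scale handed to the investigator are not linked in the text. The heading of 9.1.4.1 may lead site staff to think that a mild/moderate/severe entry already satisfies section 8.1 and the Clavien endpoint. If the case report form holds nothing else, the endpoint would rest on an intensity level that the plan does not translate into a grade.

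Relatedness matters because section 1.1 gives the safety of the Xpeeda fiber, used with defined laser settings, as one of the two things the study is meant to quantify. If likely links have no category and *Device* mentions neither laser nor fiber, the relationship column of the listing cannot cleanly answer that question. The direction of any error is unknown.

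**Working it through.** No formula or stated figure applies. The check sets the definitions side by side.

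**1. Does 9.1.4.1 yield the measure in 8.1 and 5.1.2.1?** Section 8.1 names a published classification by citation. Section 9.1.4.1 has three descriptive levels, no grade, no citation of reference 2 and no mapping. No mapping appears elsewhere in the text supplied. Applying the stated criteria therefore gives an intensity level only.

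**2. Are the levels exclusive?** Take one event that interferes with activity, needs treatment and leaves sequelae, without marked discomfort.

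| Feature | *Moderate* | *Severe* |
|---|---|---|
| Interferes with activity | allowed (may interfere): met | met; discomfort and interference are joined by and/or, so interference is enough |
| Needs treatment | required: met | required: met |
| Sequelae | allowed (may have): met | required: met |
| Fits? | yes | yes |

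One event fits two levels. There is a second, weaker overlap. *Mild* has two limbs joined by *or*, the first being simply no interference. An event that does not interfere but needs treatment meets that limb and can also meet *Moderate*.

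**3. Is there a relatedness category for a likely link?** Take an event whose link is judged likely but open to real doubt.

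- *Definitely Related* requires that there be at most slight doubt: not met.
- *Possibly Related* requires that the link be rather improbable: not met.
- *Not Related* requires that no plausible association exist: not met.
- *Unknown* requires that information be lacking: not met.

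No category is valid. Section 9.1.4.4, which concerns diagnoses, counts a *possible* diagnosis among those held with relative certainty. The protocol thus uses the word in opposite senses in adjacent subsections.

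**4. Is *Device* defined by the device?** In 9.1.4.2 it is limited to events attributable to the vaporization procedure, and neither laser nor fiber is named. Section 9.1.2 refers to use of the device. Section 9.3.1 describes its procedure-related list as related to the vaporization procedure too. Two phrases hint at the intended split: *Procedure* in 9.1.4.2 applies regardless of how the fiber performs, and 9.3.1 adds that its complications arise with or without ablation. The *Device* line itself does not state the split.

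**5. Reach.** Primary safety bullets: 5 in 5.1.2.1 + 9 in 5.1.2.2 = 14. Bullets that use Clavien: 1. The remaining 14 − 1 = 13 are named by event type or measurement and need no severity grade.

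**The case against.** **The Clavien wording may be an adaptation.** Section 8.1 says modified, and the heading of 9.1.4.1 says based on Clavien, so the three levels could be the study's own version. The documents do not reproduce reference 2, so they cannot show that 9.1.4.1 departs from it. This stands as a limit on the claim, but it does not remove the defect. If 9.1.4.1 is a separate scale, the mapping is missing. If it is the study's Clavien scale, the endpoint is measured on overlapping levels.

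**Grades can still be assigned.** A reader might infer that the Clavien endpoint is unobtainable. The documents do not support that. Section 9.1.3 already requires treatment and outcome for each event, section 8.1 points to the source, and the form, which is not in the supplied text, may already hold a Clavien field.

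**The overlap is modest.** An ordinary ordinal reading would place the test event at *Severe*. That is reasonable, but the protocol does not state it; a one-line tie-break would do so.

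**Event types on both anticipated lists.** Capsule perforation and bleeding appear in both 9.3.1 and 9.3.2, and a reader might infer that attribution is unreliable for them. That does not follow. The lists name event types that can arise from either cause, and 9.1.4.2 attributes each event individually. The fault is in the *Device* definition.

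**The study is small and descriptive.** It has 20 subjects, a listing of individual events, and no relatedness rate or safety threshold. This stands and sets the severity.

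**Conclusion.** The point holds as a minor defect in definitions. Followed literally, section 9.1.4 does not produce the measure named in 8.1 and 5.1.2.1, allows two severity levels for one event, has no valid category for a likely link, and does not tie *Device* to the device. The effect is confined to the Clavien endpoint (1 of 14 primary safety bullets) and to the severity and relationship fields of the listing. No effect on event counts can be calculated. The finding rests on the protocol text alone, because the form cannot be checked.

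Two wider inferences are not supported:

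- **Serious-event reporting.** A reader might think it is compromised. Reporting to the monitor under 9.2.1 depends on seriousness, not on these scales, and 9.1.3 notes that "The term serious is not synonymous with severity". There is a terminology slip: 10.14 is triggered by a severe adverse device effect, and the heading of 9.2.1 expands SAE with *Severe* where section 12 has *Serious*. The body of 9.2.1 says serious, and 10.14 tells unsure staff to call the monitor, so this is a side item.
- **Events already graded.** A reader might combine the planned January 2016 start with the June 2016 revision date and conclude that events had been recorded before this revision. Actual enrollment dates are not given, so this remains unknown.

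**What to change.** 1. **Severity (9.1.4.1 and the adverse event form).** Record the modified Clavien grade of reference 2 for each event in its own field, unless the form already has one, using the treatment and outcome data that 9.1.3 already requires. Remove the Clavien label from the intensity heading, or state the mapping. Make the intensity levels mutually exclusive.
2. **Relatedness (9.1.4.2).** Remove the restriction to unlikely links from *Possibly Related*, or add a *Probably Related* level. Define *Device* as attributable to the laser or fiber, in line with 9.1.2.
3. **Reporting.** Use one written grading rule in both the interim and the final report, and flag any grade assigned retrospectively.
4. **Terminology.** Reconcile *severe* in 10.14 and in the heading of 9.2.1 with *serious* in 9.1.3.

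**Cost.** Wording changes and at most one or two form fields, with no extra visits or procedures. The grade table of reference 2 must be at hand, any events already recorded need one regrading pass, and device-related counts may move in either direction.

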##### 9.1.4.2 Relationship of AE to the Device

Each adverse event should be assessed for its relationship to the device or procedure as identified as follows:

- **Device:** This category should be restricted to adverse events directly attributable to the vaporization procedure
- **Procedure:** This category should be restricted to adverse events inherent to the procedure irrespective of the fiber performance.

Use the following categories for assigning the certainty of the relationship:

- **Definitely Related:** An AE is definitely related if it is obvious, certain or there is little doubt regarding the relationship
- **Possibly Related:** An AE is possibly related if it is capable of being related but relatively unlikely.
- **Not Related:** An AE is not related if it is determined that there is no plausible association.
- **Unknown:** Use this term if there is insufficient information to determine if the AE is related to the device or procedure.

##### 9.1.4.3 Pre-existing Conditions

A pre-existing condition should not be reported as an adverse event unless there has been a substantial increase in severity or frequency of problems, which has not been attributed to natural history.

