## **9 Adverse Events (AE)**

### **9.1 Adverse Events Definitions**

#### **9.1.1 Adverse Event**

Any untoward medical occurrence, unintended disease or injury, or untoward clinical signs (including abnormal laboratory findings) in subjects, users or other persons, whether or not related to the investigational medical device

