## 9.2 Reporting

### 9.2.1 Adverse Events (AE) and Severe Adverse Events (SAE) Reporting

All serious adverse events, whether or not deemed expected or device-related, must be reported to the clinical monitor immediately or within 24 hours of knowledge by telephone (see below). A written report must follow within five (5) working days and is to include a full description of the event and sequence. If the Lumenis monitor cannot be reached, the site personnel will directly contact the Lumenis Communication Center (USA) at [contact].

If an anticipated adverse event occurs at any time during or after the use of the study device, the Investigator must report it to Lumenis. If the anticipated adverse event, in the opinion of Lumenis or the Investigator, is likely to affect the safety of the subjects or the conduct of the study, the IRB/ethic committee will be notified of the effect as required by the authorized representative.

The Investigator shall report to the EC and regulatory authorities serious adverse events and device deficiencies that could have led to a serious adverse device effect, if required by the national regulations or by the EC.

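### Section 9.1.4.3 exempts a substantial worsening from adverse event reporting once it is attributed to natural history, in conflict with 9.1.1, 9.1.3, 9.1.4.2 and 9.2.1

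*Combined protocol and SAP*

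**What the plan says.** Section 9.1.4.3 says that a pre-existing condition should not be reported as an AE "unless there has been a substantial increase in severity or frequency of problems, which has not been attributed to natural history". It names no one to make the attribution and gives no criteria for it.

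Four other sections bear on the same event:

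- **9.1.1** defines an AE as "Any untoward medical occurrence, unintended disease or injury, or untoward clinical signs (including abnormal laboratory findings) in subjects, users or other persons", and adds "whether or not related to the investigational medical device".
- **9.1.3** opens its definition with "A serious adverse event is any event that" and then lists outcome criteria, among them in-patient or prolonged hospitalization. None refers to cause. The same section also has a rule on entries in the source document and on the CRF, which begins "Any adverse events or complications reported by the patient or observed by the physician that occur during or after treatment with the device will be".
- **9.1.4.2** supplies a grade for events without a causal link: "An AE is not related if it is determined that there is no plausible association".
- **9.2.1** says "All serious adverse events, whether or not deemed expected or device-related, must be reported to the clinical monitor immediately or within 24 hours". It also requires anticipated AEs to be reported to the sponsor.

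Section 5.1.2.2 names urinary retention, urge incontinence, re-catheterization and readmission for a secondary operation among the primary safety endpoints. Section 8.1 plans a listing of the AEs that were reported, including their possible relationship to treatment.

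**The concern.** It is ordinary practice not to report a stable baseline condition as an AE, and that part of 9.1.4.3 is not in question. The closing clause goes further. It makes an opinion about cause a condition for reporting at all, even where a substantial worsening has been documented. Elsewhere the protocol treats cause as something graded on an event already reported.

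This matters more here than in most studies, because the study disease is itself the pre-existing condition. Under 6.2.1 every subject has an enlarged prostate, an AUA score of at least 12 and Qmax below 15 mL/s. Several 5.1.2.2 items can be expressions of that disease as well as complications of surgery. The study has a single arm, so no comparator group exists against which a natural-history attribution could be checked.

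The clause can take events out of the AE listing but cannot add any. If it has an effect, the AE profile looks more favourable than it was. Safety is part of the primary objective.

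**Working it through.** The plan states no safety rate, threshold, power or confidence interval, so there is no figure of its own to reproduce. The check is a comparison of the rules, followed by a sense of scale.

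**1. One event under each rule.** Take a man with a urinary problem documented at baseline. It worsens substantially after treatment, and the worsening is attributed to the natural history of BPH.

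| Section | Is it reported? |
|---|---|
| 9.1.1 | Yes. It is an untoward occurrence, and cause is irrelevant. |
| 9.1.4.2 | Yes. It is reported and may be graded Not Related. |
| 9.1.3 and 9.2.1, if it leads to hospitalization | Yes. It meets a seriousness criterion and goes to the monitor within 24 hours. |
| 9.1.4.3 | No. The attribution removes it. |

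The answers differ, and no section sets an order of precedence.

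**2. Where the event would show.** Section 8.1 lists only reported AEs. In Table 1, Adverse Event Assessment is the only row that would pick up retention, re-catheterization or readmission as events. PVR, Qmax, AUA and QoL are measured at baseline and at 1 and 3 months whatever is reported, so a worsening in those measures remains visible there, though not as an AE.

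**3. Scale.** Input: n = 20 (6.1). The event counts below are assumptions, since the documents give none.

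- Each omitted event changes a proportion by 1/20 = 5 percentage points.
- Exact (Clopper-Pearson) 95% limits for x events in 20 are the beta quantiles B(0.025; x, 21 − x) and B(0.975; x + 1, 20 − x). For x = 0 the lower limit is 0 and the upper is 1 − 0.025^(1/20) = 16.8%.

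| Events listed | Proportion | Exact 95% limits |
|---|---|---|
| 2/20 | 10% | 1.2% to 31.7% |
| 1/20 | 5% | 0.1% to 24.9% |
| 0/20 | 0% | 0% to 16.8% |

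If two such worsenings occurred and one was left out, the listed rate would fall from 10% to 5%. If both were left out, it would be 0%.

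**4. How often the clause could come into play.** If the true probability per subject of such a worsening were 5%, 10% or 15% (assumed), the chance of at least one among 20 is 1 − (1 − p)^20:

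- p = 5%: 1 − 0.95^20 = 64%
- p = 10%: 1 − 0.90^20 = 88%
- p = 15%: 1 − 0.85^20 = 96%

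This is the chance that an eligible event occurs, not that it is attributed to natural history. The documents give no basis for the latter.

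**The case against.** A reader might infer that treatment failures drop out of the safety result, or that a serious worsening escapes the 24-hour report. The documents do not support either reading, for these reasons:

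- The 5.1.2.2 items are named endpoints with no natural-history exemption, and 8.2 says all endpoints will be analyzed. Section 9.1.4.3 governs only what is reported as an AE.
- Section 9.1.3 covers any event that meets a criterion, and 9.2.1 requires every serious event to be reported. On that wording a worsening that leads to hospitalization stays reportable.
- Section 9.3.1 lists retention, urgency, urge incontinence, dysuria, hematuria and infection as anticipated procedure-related events, and 9.2.1 requires anticipated AEs to be reported. Calling them natural history within 3 months of surgery would go against the protocol's own classification.
- The clause concerns pre-existing conditions. New retention in a man who did not have it at baseline falls outside it. Section 6.2.2 excludes PVR above 300 mL, and current retention combined with Pdet below 40 cm H2O. Some men with retention could still enter, but they would not be the general case.
- Section 9.1.4.3 does not say who attributes cause. That it would be the investigator is an inference from 9.1.3, which gives the investigator the relatedness decision.

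All of this stands, and it narrows the consequence. It does not remove the conflict: these points describe what a site would do if it followed the other sections, while 9.1.4.3 tells it to do otherwise for a worsening of a pre-existing condition.

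Nor is there a case for reporting every increase over baseline. Nothing in the documents shows the threshold of a substantial increase to be wrong. With symptomatic subjects and anticipated post-operative urgency and dysuria, dropping it could add many AEs.

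**Conclusion.** The contradiction is in the text and should be resolved. As written, 9.1.4.3 removes a substantial worsening of a pre-existing condition from AE reporting on attribution alone, contrary to 9.1.1, 9.1.3, 9.1.4.2 and 9.2.1, and nothing says which prevails.

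The consequence is a route to under-reporting that the wording permits, not a demonstrated or certain loss. It applies to worsening of pre-existing urinary problems in the 8.1 AE listing. Its direction is known, toward a safer result, and its size is 5 percentage points per omitted event. That size assumes all 20 treated subjects form the denominator; the number of omitted events cannot be estimated from the documents.

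**What to change.** Four changes:

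1. In 9.1.4.3, delete the closing clause about attribution to natural history and keep the threshold of a substantial increase in severity or frequency.
2. State that an opinion that the worsening is natural history is recorded only in the relatedness field of 9.1.4.2 and has no bearing on whether the event is reported.
3. State that any event meeting 9.1.3 is reported under 9.2.1 whatever its attributed cause.
4. State that the 5.1.2 items are counted whatever their attributed cause.

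The cost is a short protocol amendment, with IRB/EC approval under 10.10, and possibly a few more AEs listed as Not Related, so the AE listing may look slightly less favourable. No visit, measurement or sample-size change is needed.

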##### 9.1.4.4 Diagnosis

There should be an attempt to report a "diagnosis" rather than the individual signs, symptoms and abnormal laboratory values associated with the diagnosis. However, a diagnosis should be reported only if, in the Investigator's judgment, it is relatively certain (i.e., definite or possible). Otherwise individual signs, symptoms and abnormal laboratory values should be reported as the adverse events.

**Description: Surgical. Protocol LUM-SBU-VP-15-02, Ablation efficacy of contact side firing fiber in predefined settings for treating BPH**

